#### 1.0 SUMMARY OF STUDY (Abstract with a maximum of 300 words)

Obstructive sleep apnea (OSA) has been estimated to affect between 2 and 4% of the U.S. population < Young T, NEJM 1993>. It is a serious, lifethreatening condition associated with obesity, hypertension, congestive heart failure, pulmonary hypertension, coronary artery disease, and cardiac arrhythmias and has an 8 year mortality rate of nearly 40% < Parrish JM, Mayo Clin Proc 2004, He J, Chest 1988>. Following general anesthesia, patients with OSA have been noted to have a significantly increased risk of respiratory complications, morbidity and mortality < Gupta RM Mayo Clin Proc 2001, Liao P, Sleep 2007, Young T, Sleep 2007, Marshall NS, Sleep 2008 >. This may be due to residual effects of inhaled anesthetics which can decrease upper pharyngeal muscle tone leading to airway compromise in OSA patients <Bell RL, Anes Clin of NA 2005>. Also, OSA patients are exquisitely sensitive to the ventilatory depressant effects of postoperative opioids, causing decreased responsiveness to hypercarbia and episodic arterial hypoxemia <Ostermeier AM, Anes Anal 1997, Stoelting, Anesthesia and Coexisting Disease 4th ed>. Currently, there is not a well-established, general anesthetic technique that will decrease the risk of complications in OSA patients. The objective of this study is to compare the postoperative recovery profile of OSA patients receiving standard Sevoflurane inhaled anesthesia versus Sevoflurane combined with a low-dose ketamine infusion.

#### 2.0 BACKGROUND & RATIONALE

Obese patients are known to have a delayed emergence from anesthesia due to volatile gases' high affinity for adipose tissue. Also, adipose tissue serves as a depot for anesthetic gases during prolonged exposure <Miller's Anesthesia, 6th ed>. In addition, many obese patients presenting for surgery meet clinical screening criteria for obstructive sleep apnea <Chung F, Anesthesiology 2008>. Surgical patients with obstructive sleep apnea patients are known to be very sensitive to the respiratory depressant effects of intravenous opioids in the postoperative period <Ostermeier AM, Anes Anal 1997, Stoelting, Anesthesia and Coexisting Disease 4th ed>. When possible, opioids should be avoided in favor of nonsedating agents such as acetaminophen, ketorolac or even regional anesthesia when possible. Unfortunately, after major surgery, most patients will still require IV opioids titrated to effect in order to adequately control their pain.

Ketamine is a dissociative anesthetic agent that provides profound analgesia without depressing the respiratory system <Miller's Anesthesia, 6th ed>. Ketamine is extensively metabolized by hepatic p-450 enzymes to a weak, water-soluble compound that is excreted by the kidneys and has a short context-sensitive half-time (time for plasma level to drop by 50%) even during prolonged infusions <Barash, Clinical Anesthesiology, 4th ed>. Multiple studies have demonstrated that intraoperative, subanesthetic

dosing of ketamine can significantly reduce postoperative opioid requirements following major surgery <Bell RF, Cochrane Review, 2005>. This low-dose of ketamine was also shown to decrease the incidence of posterative nausea and vomiting and was not associated with an increase adverse pyschotrophic effects. None of these studies targeted obstructive sleep apnea patients to determine whether these opioid-sparing effects persist and could mitigate the postop respiratory compromise or improve their overall recovery profile.

## 3.0 SIGNIFICANCE OF STUDY

Obstructive sleep apnea (OSA) affects millions of people in the U.S., and currently, there is not a well-established, general anesthetic technique that clearly decreases the risk of postoperative respiratory complications in these patients. If OSA patients in our study group have significantly decreased postoperative opioid requirements and improved recovery profiles in the PACU, our protocol could have significant implications in defining future standardized general anesthesia recommendations for patients with this disease. Ultimately, the aim of this study is to substantially reduce overall postoperative morbidity and mortality associated with obstructive sleep apnea.

#### 4.0 OBJECTIVE(S) & HYPOTHESIS

Obstructive sleep apnea (OSA) has been estimated to affect between 2 and 4% of the U.S. population < Young T, NEJM 1993>. It is a serious, lifethreatening condition associated with obesity, hypertension, congestive heart failure, pulmonary hypertension, coronary artery disease, and cardiac arrhythmias and has an 8 year mortality rate of nearly 40% <Parrish JM, Mayo Clin Proc 2004, He J, Chest 1988>. Following general anesthesia, patients with OSA have been noted to have a significantly increased risk of respiratory complications, morbidity and mortality <Gupta RM Mayo Clin Proc 2001, Liao P, Sleep 2007, Young T, Sleep 2007, Marshall NS, Sleep 2008 >. This may be due to residual effects of inhaled anesthetics which can decrease upper pharyngeal muscle tone leading to airway compromise in OSA patients <Bell RL, Anes Clin of NA 2005>. Also, OSA patients are exquisitely sensitive to the ventilatory depressant effects of postoperative opioids, causing decreased responsiveness to hypercarbia and episodic arterial hypoxemia <Ostermeier AM, Anes Anal 1997, Stoelting, Anesthesia and Coexisting Disease 4th ed>. Currently, there is not a well-established, general anesthetic technique that will decrease the risk of complications in OSA patients. The objective of this study is to compare the postoperative recovery profile of OSA patients receiving

standard Sevoflurane inhaled anesthesia versus Sevoflurane combined with a low-dose ketamine infusion.

We hypothesize that the group of obstructive sleep apnea patients that receive low-dose intraoperative ketamine will report lower pain scores, require less supplemental intravenous Morphine, and have less frequent side effects and desaturation episodes post-operatively than the group receiving saline.

#### 5.0 INTERPRETATION OF EXPECTED RESULTS

Statistical analysis with a priori power analysis was performed to determine the number of patients per group sufficient to detect a decrease of >30% in postoperative opioid requirements on the basis of the results of Kararmaz et al., Anesthesia and Analgesia 2003. With a power of 80% and a type 1 error of 5%, it was estimated that 32 patients will be required per group. We will plan to enroll 65 patients total to account for unanticipated subject dropout. Mann-Whitney U-test will be used to compare VRS, modified Aldrete, and patient satisfaction scores. Student's t-test will be used to compare BMI, time to first analgesic, number of analgesic demands, amount of analgesic consumption and ODI. The X2 test will be used to compare frequency of side effects, race and sex distribution. The resulting values will be expressed as mean +/- SD or median and range with P< 0.05 considered statistically significant.

#### 6.0 ELIGIBILITY & EXCLUSION CRITERIA

Inclusion criteria: Total of sixty-five patients, aged 19-70, scheduled to undergo laparoscopic gastric bypass surgery for morbid obesity. Patients should have a diagnosis of obstructive sleep apnea as confirmed by sleep study and are not currently using a CPAP devise. If no sleep study is available, patients should have the 4 clinical predictors of obstructive sleep apnea as described by STOP (Snoring, Tiredness during daytime, Observed apnea, high blood Pressure) screening questionnaire. <Chung, F Anesthesiology 2008>

Exclusion criteria: Patients <19 yrs, positive pregnancy test, ASA> III, history of alcohol or narcotic abuse in last 90 days, significant cardiovascular or respiratory disease (baseline oxygen saturation below 92%), significant psychiatric or neurologic disease, history of significant hepatic or renal disease (baseline creatinine>1.5), history of allergy or contraindication to anesthetic agents or ketamine including patients with increased ICP, increased IOP, severe arrhythmias, history of delirium, hallucinations, or psychosis, or history of uncontrolled seizures, or potential risk for malignant hyperthermia (family history), history of difficult intubation that would preclude standard induction of anesthesia, prisoners, persons who are mentally impaired, and non-english speakers.

Criteria for early withdrawal for the study: <2 hrs surgical time, any surgical or anesthetic complication that prevents the assessment of study variables, clinically relevant residual neuromuscular blockade or other reason for patient to require prolonged tracheal intubation following surgery.

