Anesthesia will be maintained in the both groups with inhaled Sevoflurane starting at 4% end-tidal concentration and titrated to keep the bispectral index (BIS) value at 40-50 (Bispectral Index, Aspect Biomedical, Natick, MA). After induction and before surgical incision is made, patients will receive an intravenous bolus saline or the study drug, S(+) ketamine 0.5mg/kg IBW bolus followed by a continuous infusion of 0.5 mg/kg/hr (IBW) using a Baxter syringe pump. The infusion will be stopped at the closure of the abdominal fascia layer, approximately 30 minutes before the end of surgery. In both groups, neuromuscular blockade will be maintained with rocuronium and titrated to train-of-four (TOF) ratio until the abdominal fascia is closed. Oxygen, air (no nitrous oxide), IV fluids, vasoactive drugs, and fentanyl (up to 5mcg/kg IBW) will be titrated at the anesthesiologist's discretion to maintain hemodynamics at 25% of baseline. Glycopyrolate and neostigmine will be given to facilitate reversal of neuromuscular blockade. Sevoflurane will be discontinued immediately prior to completion of surgery. All patients will receive IV ketorolac 30mg at conclusion of closure of abdominal fascia. Endotracheal tube will be removed when patient meets extubation criteria (spontaneous breathing with min 6ml/kg IBW tidal volume, following commands with ability to sustain hand grip and 5-sec head lift). All patients will then be discharged from the operating room to the post-anesthesia care unit (PACU).

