Upon arrival in the PACU, all patients will be monitored according to standard post-anesthesia protocols for a period of at least 2 hours. The PACU nurse that is blinded to treatment group will assess and record baseline vital signs including HR, BP, RR, SpO2, and VRS score. Modified Aldrete score including presence of nausea/vomiting, sedation level or evidence of dysphoria will be recorded at 15 minute intervals. SpO2 will be monitored continuously with documentation of oxygen flow required to maintain oxygen saturation of at least 94%. As per PACU protocol, initially patients will receive oxygen 40% by open face mask, with weaning to NC or RA, maintaining SpO2 > 94%. Desaturation episodes will be scored automatically by pulse oximetry analysis software (Nellcor, NPB-290). Data evaluated will include: comparison of patient demographics, time to first analgesic, number of analgesic demands, amount of analgesic consumed in the OR and PACU, frequency of side effects, and ODI (oxygen desaturation index). ODI is defined as the number of desaturations (lower than 4% from baseline) per hour of recording, which correlates with PSGdetermined apnea/hypopnea index and can be used as an indicator of postoperative apneic episodes <Ahmad S, Anesthesia and Analgesia 2008>}. Time to first analgesia request will be recorded and pain (VRS >/= 4) will be treated with intravenous morphine 2mg. This will be repeated at 5 minutes intervals until pain score improves or patient has untoward side

effects, at which time the PACU physician should be immediately called to the patient's bedside. Further monitoring for of patients in PACU or on the floor may be indicated in some patients according to the discretion of the attending anesthesiologist and surgeon; however it is not mandatory for this study. According to Terris et al., "Significant complications [of OSA] generally emerge within 2 hours after surgery. Therefore a decision regarding the level of postoperative monitoring needed may be made with confidence during the period of time that the patient is in the recovery room" <Terris DJ, Laryngoscope 1998>.

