# 11.0 STATISTICAL CONSIDERATIONS

Statistical analysis with *a priori* power analysis was performed to determine the number of patients per group sufficient to detect a decrease of >30% in postoperative opioid requirements on the basis of the results of Kararmaz et al., Anesthesia and Analgesia 2003. With a power of 80% and a type 1 error of 5%, it was estimated that 32 patients will be required per group. We will plan to enroll 65 patients total to account for unanticipated subject dropout. Mann-Whitney U-test will be used to compare VRS, modified Aldrete, and patient satisfaction scores. Student's t-test will be used to compare BMI, time to first analgesic, number of analgesic demands, amount of analgesic consumption and ODI. The X2 test will be used to compare frequency of side effects, race and sex distribution. The resulting values will be expressed as mean +/- SD or median and range with P< 0.05 considered statistically significant.

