#### 13.0 REPORTING ADVERSE EVENTS

Patients at risk for severe adverse reactions will be excluded from the study. This includes patients with a history of adverse reaction to ketamine, patients with increased ICP, increased IOP, arrhythmias, history of delirium, hallucinations, or psychosis, or history of uncontrolled seizures.

Patient will be removed from the study if any surgical or anesthetic complication necessitates deviation from routine anesthetic management or prevents the assessment of study variables. Also, patient will be withdrawn if clinically relevant residual neuromuscular blockade or other reason for patient to require prolonged tracheal intubation following surgery.

Any adverse events occurring in the enrolled study subjects will be immediately reported to the UAB Department of Anesthesiology Human Subjects Research Committee and the UAB IRB. As an integral element of data and patient safety monitoring, a completed departmental-level Data Protection and Patient Safety Monitoring Form will be presented to the UAB Department of Anesthesiology Human Subjects Research Committee every three months.

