# If study involves drugs or devices skip Items 19.b. and 19.c., go to Item 20, and complete the Drug or Device Review Sheet, as applicable.

- b. If hazards to an individual participant occur, describe (i) the criteria that will be used to decide whether that participant should be removed from the study; (ii) the procedure for removing such participants when necessary to protect their rights and welfare; and (iii) any special procedures, precautions, or follow-up that will be used to ensure the safety of other currently enrolled participants.

  Criteria for early withdrawal for the study: <2 hrs surgical time, any surgical or anesthetic complication that prevents the assessment of study variables, clinically relevant residual neuromuscular blockade or other reason for patient to require prolonged tracheal intubation following surgery.
- c. If hazards occur that might make the risks of participation outweigh the benefits for all participants, describe (i) the criteria that will be used to stop or end the entire study and (ii) any special procedures, precautions, or follow-up that will be used to ensure the safety of currently enrolled participants.

  The overall study will be suspended if is determined that, at any point, study procedures are not adequate to protect the participant's safety. All efforts will be made during procedures to ensure that the participant's risk is minimized.

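### Randomised patients are withdrawn for events after allocation, with no analysis set and no follow-up rule, so outcomes that could be measured may leave the comparison

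*Combined protocol and SAP*

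**What the plan says.** Section 6.0 of the protocol lists these criteria for early withdrawal: "<2 hrs surgical time, any surgical or anesthetic complication that prevents the assessment of study variables, clinically relevant residual neuromuscular blockade", or another reason for prolonged intubation after surgery. Residual blockade is most naturally read there as one cause of prolonged intubation.

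Section 13.0 repeats the intubation rule, omits the 2-hour rule, and widens the complication rule: "Patient will be removed from the study if any surgical or anesthetic complication necessitates deviation from routine anesthetic management", or if the complication prevents assessment. The first limb applies even when every outcome can be measured.

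Item 19.b of the human subjects form, submitted to re-open the study, repeats the section 6.0 list, beginning "Criteria for early withdrawal for the study: <2 hrs surgical time". The heading above it says "If study involves drugs or devices skip Items 19.b. and 19.c., go to Item 20" and sends drug studies to a separate review sheet that is not in the supplied text. The point therefore rests on sections 6.0 and 13.0.

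Sections 5.0 and 11.0 carry the same statistical text: a sample size, a list of tests and a P threshold. They name no analysis set and no missing-data rule. The only related provision is "We will plan to enroll 65 patients total to account for unanticipated subject dropout", against 32 required per group. The re-opened form gives 150 participants (items 15.a and 15.d).

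**The concern.** Allocation and the start of study drug come before any of these triggers can be known. Section 8.0 gives the bolus and starts the infusion before incision; surgical duration, complications and extubation follow. Withdrawal on such events, if it means removal from the analysis, leaves two groups that are no longer the groups formed by randomisation.

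The triggers do not carry the same risk. Surgery under 2 hours is unlikely to depend on the study drug, so that rule mainly loses data. Complications and prolonged intubation could depend on treatment, and they bear on the recovery profile that the trial sets out to compare (section 4.0). Removing those patients could favour either arm.

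Part of the loss would also be avoidable. A patient with a short operation, or one with a management deviation who is extubated, goes to the PACU like any other. There, section 8.0 says that "all patients will be monitored according to standard post-anesthesia protocols for a period of at least 2 hours", with pain score, Aldrete score, analgesic use, side effects and ODI recorded.

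**Working it through.** **1. Which triggers discard measurable outcomes**

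| Trigger | Source | Outcomes still measurable? |
|---|---|---|
| Surgery under 2 hours | 6.0, item 19.b | Yes: PACU and 24-hour outcomes |
| Complication that prevents assessment | 6.0, 13.0, item 19.b | No for the affected outcomes, by definition |
| Complication requiring deviation from routine management | 13.0 only | Yes, if the patient is extubated |
| Prolonged intubation, including from residual blockade | 6.0, 13.0, item 19.b | PACU pain score, time to first request and PACU ODI are undefined while intubated; 24-hour data may be obtainable |

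The 24-hour assessment (section 8.0; form item 16) covers vital signs, pain score, morphine use and satisfaction, and makes no exception for withdrawn patients. No text says that it is to be completed for them.

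**2. The plan's sample size**

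Inputs from section 11.0: 32 per group, 80% power, 5% type 1 error, a decrease of more than 30% in opioid requirement. No mean, SD or sidedness is given, so the figure cannot be reproduced, only solved backwards. For a two-sided t-test at 5%, 32 per group gives 80% power at a standardised difference d = 0.711. A 30% decrease then implies SD/control mean = 0.30/0.711 = 0.42.

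**3. Power if withdrawn patients are not analysed**

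Per-arm size is n = N(1 − w)/2, where N is the number enrolled and w the fraction withdrawn; d = 0.711, two-sided 5%. The values of w are assumptions.

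| w | N = 65: n per arm | Power | N = 150: n per arm | Power |
|---|---|---|---|---|
| 0% | 32.5 | 80.6% | 75 | 99.1% |
| 5% | 30.9 | 78.5% | 71.25 | 98.8% |
| 10% | 29.25 | 76.3% | 67.5 | 98.4% |
| 20% | 26 | 71.1% | 60 | 97.2% |

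The allowance is 65 − 64 = 1 patient, or 1/65 = 1.5%. Keeping 64 analysable would need 64/0.95 = 67.4 (68), 64/0.90 = 71.1 (72) or 64/0.80 = 80 enrolled.

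**4. Direction of bias for opioid use**

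This is a deliberately unfavourable illustration: no true effect, normally distributed opioid use, and the withdrawn patients are the highest users. After removing the top fraction w, the arm mean moves by −φ(z)/(1 − w) SD, where z is the 1 − w quantile of the standard normal and φ its density.

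- w = 10%: −0.195 SD
- w = 5%: −0.109 SD
- 10% withdrawn on ketamine and 5% on control: −0.195 + 0.109 = −0.09 SD, a false advantage for ketamine
- The reverse: +0.09 SD
- Equal fractions: no shift

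The documents give no withdrawal rates, so this shows direction and rough scale only.

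**The case against.** The strongest reply is that the documents nowhere say that withdrawn patients are left out of the analysis. PACU monitoring is for all patients and the 24-hour assessment has no exception. That is correct, and a reader who infers a stated exclusion goes further than the text. But sections 6.0 and 13.0 do state a removal rule, and nothing in section 11.0 brings those patients back. Leaving the matter open is itself the defect.

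A reader might also infer that complications in withdrawn patients vanish. They do not: section 13.0 requires adverse events in enrolled subjects to be reported at once to the departmental committee and the IRB, with a monitoring form every three months. What is not assured is that they enter the comparison by arm.

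Nor does every trigger discard usable data. The complication rule of section 6.0 alone covers only unassessable cases, and nausea, dysphoria or PACU desaturation is not in itself a trigger. Sections 6.0 and 13.0 can be read as cumulative rather than contradictory, but the wider rule in one is absent from the other, so they need harmonising.

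The design is double-blind, which makes unequal withdrawal less likely. It does not exclude it, because drug-related events could themselves lead to withdrawal, and no text says who judges that a deviation has occurred. Finally, the power loss belongs to the 65-patient plan; at 150 it is small. All of this limits the size of the point without removing it.

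**Conclusion.** The point holds in a limited form and should be fixed. The plan withdraws randomised, ordinarily already dosed, patients for later events, and does not say that they are followed or analysed. For short surgery, and for management deviations in extubated patients, that puts at risk outcomes already scheduled for collection.

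The two consequences should be kept apart. The 2-hour rule is probably non-differential and costs precision: a few points of power with 65 enrolled, little with 150. Removal for complications or prolonged intubation could be differential, and a larger sample does not cure that. Its size cannot be derived from the documents; the 0.09 SD above is an unfavourable illustration, set against an implied design effect of 0.71 SD.

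The power figures assume a two-sided t-test and an effect solved back from 32 per group. A conclusion that the re-opened trial is underpowered because of withdrawals is not supported. The finding that no analysis set or follow-up rule exists covers the supplied text only.

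**What to change.** 1. Reconcile the withdrawal wording of sections 6.0 and 13.0 and item 19.b, and separate stopping study procedures from leaving follow-up and analysis.
2. State in section 11.0 that all randomised patients are analysed in their assigned group, and that neither an actual surgical time under 2 hours nor a management deviation removes a patient whose outcomes can be measured.
3. For withdrawn patients, complete the existing PACU record where possible and the existing 24-hour form. Record outcomes that cannot be assessed as missing, with the reason.
4. Report withdrawals with reasons, complications and prolonged intubation by arm.
5. Use the current withdrawal rules only to define a per-protocol sensitivity analysis.

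The cost is wording in three places and in section 11.0, one sensitivity analysis, one table by arm, and existing forms completed for a few more patients. No new visit or measurement is needed and clinical care is unaffected. The downside is slight dilution of the treatment effect from short or complicated cases.
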